A non-contrast cervical spine CT scan at will be obtained for research purposes at UVMMC at the 12 (+/-1) week time point. Final fracture characteristics (angulation, displacement) will be documented based on the 12-week CT scan. Amount of fracture healing will be assessed on CT by a radiologist by the following method¹⁰: 1 mm coronal and sagittal sections across the fracture will be individually analyzed. The radiologist will reconstruct the CT scan to true orthogonal coronal and sagittal images. Each slice will be analyzed for the width of bridging bone as a percentage of the width of the fracture line. The sum total of the widths of bridging bone, divided by the sum total of the fracture widths will be expressed as a percentage of total healing for that patient. This absolute % of bridging bone will be the primary outcome¹⁰. Fracture characteristics (obliquity, angulation, displacement, comminution) on the injury CT scan will be documented for later post-hoc analysis. Additionally, we will also compare our study group results to the union rates documented in the existing literature.

Control subjects:

Our historical control group will be comprised of patients with type II odontoid fractures (defined above) who were previously treated in our spine fracture clinic. Patients will have been injured within the past ten years, and have completed 12 +/-1 weeks of hard collar immobilization. Potentially eligible historical controls will be identified by database query and chart/radiographs review of patients from the fracture clinic. A request will be made of the UVMMC Data Management Office to identify potential control subjects. Identified potential control patients will be approached as outlined under 'Consent Process', below.

If patients are interested in active study participation by coming in for a study visit (research imaging: *Control cohort A: Active control participants*), written informed consent will be obtained in person at UVMMC by designated research personnel. Consented active control subjects will then complete a CT scan of the cervical spine for comparison to those from our study group. If flexion-extension cervical XR were not obtained 11 or more weeks after initiation of hard collar treatment as part of their routine care, flexion-extension cervical XR will be obtained for the study. Additionally, these control subjects will complete VAS Neck and NDI physical function questionnaires.

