levels are meant for baseline data collection as they relate to the ability to heal fractures, and are tested with screening labs to prevent need for additional blood draws for research purposes.

AP/Lateral XR and Flex/Ext XR is a standard set of X-rays of the cervical spine used to evaluate the secondary outcome of translational motion at the fracture.

CT Cervical spine is for research purposes at the 12-week mark only. This will be used to measure fracture union rate (the primary outcome).

The DEXA scan is a low dose x-ray scan used as a screening tool recommended for all women over the age of 65. The radiation is so low (significantly lower than a chest x-ray) that this machine and radiation is not formally regulated in the United States. Many of these patients have osteoporosis at baseline and this test allows us to screen, quantify, and subsequently manage their osteoporosis. *In this study*, DEXA scans will be obtained to evaluate bone health as it relates to the ability to heal a fracture. If a patient's T-score is ≤ -2.5 at the spine or hip in a DEXA scan obtained for research purposes, the study team will notify the patient of the finding and refer her/him for follow-up care, as appropriate.

Procedures for control cohort A (active control participants)

Table 2. Research procedures for control patients who provide written consent to active study participation (control cohort A).

Item	UVMMC	Via Mail
Informed consent	X	
Neck Disability Index	X	
VAS Neck	X	
Cervical CT Scan	X	
Flexion-extension cervical x-ray	X**	
Compensation		X*

* After completion of CT scan

** The XR is only obtained for research purposes if a flexion-extension cervical x-ray was not obtained 11 or more weeks after initiation of hard collar treatment as part of their routine care.

Procedures for control cohort B (review-only control participants)

Control cohort B includes subjects who

- (a) Previously had a cervical CT scan obtained after completion of their hard collar treatment under routine care; or
- (b) do not provide written consent to active study participation but provide verbal consent to allow the study team to collect existing information that is available from their treatment in the electronic medical record; or
- (b) are deceased and are not available for informed consent

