For these control participants, the study team will collect information that is available in the electronic medical record to support analyses of available outcomes. This information includes demographic information, fracture characteristics and applicable radiographs obtained during their routine care for neck fracture.

Describe required screening procedures performed before enrollment and while on study.

Screening procedures for treatment subjects before enrollment:

At the time of spine surgical consultation, CT scans obtained for routine care will be evaluated and those patients whose fracture types meet the inclusion criteria will be approached to consider participation in the study. After consent is obtained, but prior to enrollment, patients will be screened for eligibility based on their medical history, as well as laboratory values. Laboratory values obtained for eligibility screening will include a Comprehensive Metabolic Panel, PTH and Phos. Based on medical history, Ca, PTH, and Phos levels an endocrinologist on the study team will confirm eligibility for the study prior to enrollment.

Screening procedures for treatment subjects while on study:

Cervical spine x-rays will be obtained at each clinic visit as per our routine non-operative management. These will be reviewed as outlined in Withdrawal Procedures, below.

For research involving survey, questionnaires, etc.: Describe the setting and the mode of administering the instrument and the provisions for maintaining privacy and confidentiality. Include the duration, intervals of administration, and overall length of participation.

Not applicable

Two questionnaires (VAS Neck and Neck Disability Index (NDI) physical function questionnaires) will be administered 3 times for each treatment subject (at each clinic visit: 4 weeks, 8 weeks, and 12 weeks), and once for each control subject. Together the two questionnaires can be completed in under 10 minutes.

For treatment subjects, the questionnaires are administered as part of routine care at these time points, as they are for other patients with dens fractures. The two questionnaires are integrated into our standard practice for all spine patients at clinic. The questionnaires are administered by medical staff in clinic prior to evaluation by the physician. They are completed privately by the patient and inserted into the patient's electronic health record after the visit.

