For historical comparison subjects, the questionnaires will be administered by designated study personnel in person at UVMMC. The questionnaires will be completed by the patient after written informed consent is obtained.

TYPES OF PROCEDURES (Please do not use the "other" option unless the procedure is not listed.)

Check all that apply.

	Survey (mail, telephone, in-person, on-line)		Blood drawing:	Vol. 	Over days, weeks? 	Blood will be drawn for eligibility screening, and HbA1c levels in treatment subjects only
	Medical exams/history				Type & Amt. 	See the tests listed for treatment subjects in Table 1, above.
	Deception *see below		Surgery			Collection of Urine and/or Feces
	Observation		Drug Administration			HIV Testing
	Photographs		Device Use			Ultrasound (e.g. echocardiogram)
	Audio Recording		Exercise			X Imaging (e.g. CT scan, DEXA, mammogram, PET scans, SPECT)
	Video Recording		Diet			Use of Radiation treatment
	Interviews in person or by phone		Pathology Specimens (retrospective)			Use of Radioactive substances (e.g. radiolabeled antibodies, drugs or contrasts)
	Focus Groups		Genetic Materials (DNA)*			MRI (for treatment studies)
	Review of prospective data		Questionnaires			MRI (not for treatment studies)
	Review of retrospective data		Diaries			Tissue (obtained for clinical purposes)
	Recording of Identifiable Data		Pregnancy Tests			Tissue (obtained solely for research)
	Electrocardiograms					
	Sensitive Data (criminal or sexual conduct, drug or alcohol conduct or use)			(specify): 		

*If genetic information is being collected, GINA language must be added to the consent form.

*Deception typically involves withholding information from the potential subject and would require an alteration to the consent process.

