Statistical Considerations: Delineate the precise outcomes to be measured and analyzed. Describe how these results will be measured and statistically analyzed. Delineate methods used to estimate the required number of subjects. Describe power calculations if the study involves comparisons. Perform this analysis on each of the primary and secondary objectives, if possible.

Primary outcome will be % bridging bone on CT scan at 12 weeks as described previously based on 1 mm sagittal and coronal cuts. The study radiologist evaluating the primary outcome will be blinded to patient group (treatment vs. historical control). Secondary outcomes will include VAS Neck and NDI scores, and motion on flexion/extension radiographs.

Assuming 60% nonunion rate in our historical control group and 20% in our study group, with alpha = 0.05 and 80% power, we would need to enroll 44 patients in a randomized trial (22 control, 22 study patients) to show a statistical difference. This study is intended as an initial pilot study to suggest efficacy, and further inform a future randomized controlled trial. We see 15-20 new type II dens fractures treated non-operatively per year in our fracture clinic, and estimate the initial pilot of 10 treatment patients + 12 control subjects can be completed within 2 years.

Data analysis will be based on multi-variate regression using ANOVA, with $p < 0.05$ recognized as a significant difference. Plan is for as treated analysis; if there are patients who receive only partial course of study drug for any reason, they will be evaluated descriptively as a separate group. Additionally, we will also compare our study group results to the union rates documented in the existing literature.

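### VAS Neck and NDI have no named comparison visit: treated scores end at week 13, while cohort A controls are scored once, from about 11 weeks to 10 years after fracture

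*Combined protocol and SAP*

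**What the plan says.** Statistical Considerations fixes the primary CT outcome at 12 weeks. For the rest it says: "Secondary outcomes will include VAS Neck and NDI scores, and motion on flexion/extension radiographs". Neither questionnaire is given a visit. The analysis statement, "Data analysis will be based on multi-variate regression using ANOVA", takes p below 0.05 as significant. It names no visit, no rule for choosing among repeated scores, and no term for time since injury.

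The timing has to be assembled from other sections:

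- **Treated patients.** Study Design times the clinic visits from the date of injury, every 4 (+/-1) weeks to week 12. The questionnaire paragraph under Procedures says the two instruments are "administered 3 times for each treatment subject (at each clinic visit: 4 weeks, 8 weeks, and 12 weeks), and once for each control subject".
- **Cohort A (controls who attend a research visit).** Study Design, after describing the research imaging, says: "Additionally, these control subjects will complete VAS Neck and NDI physical function questionnaires". The questionnaire paragraph adds "For historical comparison subjects, the questionnaires will be administered by designated study personnel in person at UVMMC" and "The questionnaires will be completed by the patient after written informed consent is obtained". No target time since injury is set. The control inclusion criteria require only a completed 12 (+/-1) week collar course and a fracture no more than 10 years before consent.
- **Cohort B (review-only controls).** Sources of Materials allows VAS Neck and NDI from earlier routine visits where they exist, without selecting a visit. This cohort includes patients who "are deceased and are not available for informed consent".

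**The concern.** The two groups are scored on different clocks. Treated scores stop at about week 13. A cohort A score can come from any time between the end of the collar course and ten years later. A difference in mean VAS or NDI therefore mixes any drug effect with whatever happens to neck pain and disability over that interval.

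The direction cannot be predicted from the documents. If controls go on recovering after week 12, late scores favour them and a real benefit is hidden. If non-union symptoms persist or worsen, a benefit is inflated; the Purpose section says non-union can cause pain, disability and, less commonly, neurologic decline.

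These are the only patient-reported outcomes, and the pilot is meant to suggest efficacy and inform a randomized trial. A distorted signal here could carry into that trial's design.

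**Working it through.** **The plan's own figure.** The plan gives no calculation for VAS Neck or NDI. Its only sample size, 44 patients, concerns non-union of 60% versus 20%. The arcsine formula reproduces it: h = 2·asin(√0.6) − 2·asin(√0.2) = 0.845, and n = 2·((1.960 + 0.842)/0.845)² ≈ 22 per group. It has no bearing on this point.

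**Assessment windows.**

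| Group | Source of score | Time since fracture |
|---|---|---|
| Treated | Clinic visits | 4, 8 and 12 weeks; last at 11–13 weeks |
| Cohort A | One research visit after consent | About 11 weeks to 10 years |
| Cohort B | Past routine visit, if recorded | Not stated |

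The lower limit for cohort A assumes the collar was started at about the time of injury. The upper limit is 10 × 365.25/7 = 522 weeks, which is 522/13 = 40 to 522/11 = 47 times the treated final-visit interval. For the comparison at the last treated visit, the windows share only about weeks 11–13. For a control scored later there is no treated score at the same time, so a regression term for time would extrapolate.

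**Illustration of the consequence.** Assume no drug effect, equal SDs, a two-sided t test at 0.05, and a shift of b SD in the control mean caused by timing alone. With n₁ = 10 and n₂ = 12, df = 20 and the noncentrality is b·√(10·12/22) = 2.335·b.

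| Assumed shift b (SD) | Chance of p<0.05 |
|---|---|
| 0 | 5% |
| 0.25 | 9% |
| 0.5 | 20% |
| 0.75 | 39% |
| 1.0 | 60% |

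The shift that matters is the mean over all scored controls: (cohort A share × cohort A shift) + (cohort B share × cohort B shift). The protocol gives neither the shares nor the shifts.

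**Precision of a 12-week comparison.** The 95% CI half-width in SD units is t(0.975, 8 + n)·√(1/10 + 1/n), with 10 treated and n scored controls.

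| Scored controls n | Half-width (SD) |
|---|---|
| 12 | 2.086 × 0.428 = 0.89 |
| 8 | 2.120 × 0.474 = 1.01 |
| 6 | 2.145 × 0.516 = 1.11 |
| 4 | 2.179 × 0.592 = 1.29 |

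**The case against.** The strongest reply is that this is a pilot of 10 plus 12 patients whose objective and primary hypothesis concern union. The p<0.05 sentence is generic and does not name VAS or NDI, so a formal test of them is a reasonable reading but is not stated. That is fair, and it limits the weight of the point. It does not remove it, because the scores are declared secondary outcomes and the plan does not say how the groups will be compared on them.

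A second reply is that the rejection rates depend wholly on the chosen shifts, use an unadjusted t test where the plan speaks of regression, and assume equal SDs although control scores may span years. That also stands. The rates show how sensitive such a comparison could be; they do not measure bias in this trial.

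Three stronger readings are tempting and are not supported:

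- **That 12-week scores for cohort A are already within reach in office notes.** The questionnaire paragraph does say "The two questionnaires are integrated into our standard practice for all spine patients at clinic". However, that is in the present tense, and the text under Table 1 says only that the instruments are routine in many clinic visits. Sources of Materials lists general office notes separately from VAS and NDI for treated patients and for cohort B. For cohort A it names only the study questionnaires. Using recorded cohort A scores therefore probably means adding a data source.
- **That the wording conflict over controls is evidence of confounding.** One in-person administration for every control cannot apply to a review-only cohort that includes deceased patients. Table 2 and Sources of Materials already show who does what, so this is a minor wording matter.
- **That the CT comparison is free of the timing problem because this point is confined to questionnaires.** The research CT for cohort A is also taken after consent, so no such conclusion follows.

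**Conclusion.** The point holds. Run as written, a between-group comparison of VAS Neck and NDI confounds treatment with time since injury. The direction is unknown, and adjustment for time cannot repair it for controls scored after week 13. This rests on the visit schedule and the eligibility limits, not on any assumed effect.

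The size of the bias cannot be derived, because the documents give no SD, no recovery curve, no cohort A share and no timing for cohort B scores. The range of 9% to 60% for shifts of 0.25 to 1.0 SD is illustration only, and a shift of zero (5%) is not excluded.

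The point affects secondary outcomes of a pilot. It should be corrected, but it changes neither the sample size nor the primary outcome.

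**What to change.** In Statistical Considerations:

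- Name the 12 (+/-1) week visit as the only between-group comparison for VAS Neck and NDI.
- For controls, use scores found in the health record within that window. For cohort B this is already a listed source. For cohort A, add recorded routine-care VAS and NDI to its list in Sources of Materials, where consent permits.
- Report the comparison as an estimate with 95% CI and no significance claim, whatever the number of controls scored. This avoids having to define how many scores are enough for a test.
- Report research-visit and other off-window control scores separately and descriptively, with time since injury. Do not pool them with 12-week scores or test them against those scores.

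In the questionnaire paragraph, limit the single administration and in-person completion to cohort A, so that it agrees with Sources of Materials for cohort B.

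The cost is wording, chart abstraction (control charts are already reviewed to find eligible patients) and possibly an extension of what cohort A consents to, which cannot be judged from these documents. The downside is that 12-week scores may be missing for some or many controls. The half-width would then grow from about 0.89 SD with 12 scored controls to 1.29 SD with 4, and with none the comparison could not be made.

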Eligible patients will receive standard treatment of 12(+/-1) weeks of rigid hard collar immobilization, as well as an 8-week course of PTH analog during this time. Drug will be initiated as soon after the injury as possible, and at the latest 4 weeks from injury which will allow for completion of 8 weeks of drug administration during the period of hard collar immobilization. Teaching on drug administration will be provided for enrolled patients and their caregiver, if applicable, by designated study personnel prior to drug initiation – either while inpatient, or at the outpatient endocrinology clinic visit. Treatment subjects will otherwise receive the routine care that was provided to historical controls in terms of length of hard collar immobilization spine fracture clinic follow-up and radiographic evaluation. Treatment subjects will be followed with weekly phone calls (see Table 1) by clinical personnel on the study team for the duration of the 8-week treatment.

Study participants will be followed at the spine fracture clinic according to our usual protocol every 4 weeks +/- 1 week (from the date of injury) out to 12 weeks. All patients will fill out VAS Neck and Neck Disability Index (NDI) physical function questionnaires at each clinic visit. Use of narcotic pain medication will be collected at each clinic visit under routine care.

DEXA scans will be obtained for all participants to assess baseline bone density. If a patient has had a DEXA scan for routine care within the 12 months prior to consent, that scan will be used as the baseline test and a separate test for research will not be ordered. If needed, baseline DEXA will need to be completed after consent and by time of the 12 week visit.

All radiographs for treatment subjects will be obtained as part of routine care. These include AP/Lateral at each of the 4 (+/-1) week and 8 (+/-1) week clinic visits, and Flex/Ext at the 12 (+/-1) week clinic visits. Final (12 +/-1 week) flexion/extension radiographs will be evaluated for translational motion at the fracture site measured at the posterior cortex of the dens and evaluated by the following criteria: None, Minimal (<2 mm), Moderate (2-4 mm), Mobile (>4 mm).

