Visit Time point	Screening and baseline procedures	4-week visit (within 4 weeks of fracture)	8-week visit (8 +/- 1 weeks after fracture)	12-week visit (12 +/- 1 weeks after fracture)
Informed consent	X*			
Spine Fracture Clinic visit	X (if needed for routine care)	X	X	X
Physical Exam	X	X	X	X
Neck Disability Index		X	X	X
VAS Neck		X	X	X
(Eligibility confirmed by study team after screening labs completed and before study drug administration)				
Endocrinology Clinic visit (only if the patient is not recruited while inpatient)	X*			
Study drug teaching and first dose of Tymlos	X*			
Tymlos self-administration	X* (daily for 8 weeks after drug teaching)			
CMP	X*			
PTH	X*			
Phos	X*			
HbA1c	X*			
AP/Lateral XR	X	X	X	(X if required for routine care)
Flex/Ext XR				X
CT Cervical	X			X*
DEXA	X** (by time of 12-week visit)			
Phone check-in	X* (each week +/- 2 d after first dose for the 8-week treatment period)			

* These procedures are research-driven and deviate from routine care of treatment patients in clinic.

** The DEXA scan is completed for research purposes only if not previously completed within 12 months before consent for routine care purposes.

Spine fracture clinic (and endocrinology visit, for patients not recruited in the inpatient setting) involve medical history under routine care.

Neck Disability Index and VAS Neck physical function are questionnaires given to patients during the clinic visit and prior to medical evaluation. These take less than 10 minutes to fill out, they are validated, and they are standard/routine in many clinic visits. These questionnaires will provide secondary outcome measures.

The study drug (abaloparatide) is an FDA approved medication used to treat osteoporosis. It is a daily subcutaneous injection administered by the patient. This requires patient education.

CMP, PTH, Phos, and HbA1c are laboratory tests performed by venipuncture. Blood work includes complete metabolic profile, phosphorous, parathyroid hormone, and hemoglobin A1c. Many of these patients have osteoporosis at baseline and these tests allow us to screen, quantify, and subsequently manage their osteoporosis. This blood work is standard of care for evaluation and treatment of osteoporosis. In this study, CMP, PTH and Phos will be obtained as screening labs (see Screening Procedures, below). HbA1c

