The therapeutic alternative to our study population is the treatment given to our historical controls. This treatment is with a hard collar alone (without the use of abaloparatide).

Data Safety and Monitoring: The specific design of a Data and Safety Monitoring Plan (DSMP) for a protocol may vary extensively depending on the potential risks, size, and complexity of the research study. For a minimal risk study, a DSMP could be as simple as a description of the Principal Investigator's plan for monitoring the data and performance of safety reviews or it could be as complex as the initiation of an external, independent Data Safety and Monitoring Board (DSMB). The UVM/UVM Medical Center process for review of adverse events should be included in the DSMP.

There is a risk of loss of confidentiality. The study team's procedures to mitigate this risk and promote both physical security and confidentiality of subjects' data and records are outlined in the attached Research Data Management and Safety Plan and described under 'Risks/Benefits', above.

This study will follow the UVM IRB's policies and procedures for reportable new information. Unanticipated problems will be evaluated by the PI on a rolling basis and reported per IRB requirements.

The study does not have an external, independent Data Safety and Monitoring Board. A Data Safety Officer will be delegated responsibility for independent data validation (verification against source documentation). Data validation will be performed once annually.

Define criteria to be used for decision making regarding continuation, modification, or termination of the entire study (not individual participation) (i.e. "stopping rules").

Decision-making for the entire study: Modification or termination would be considered if there are repeated and severe adverse events attributed to the study drug. Based on study profile, the team believes this would be unlikely.

At both the participant and study levels, decisions regarding continuation/modification/termination will be at the discretion of the PI.

What will be the frequency of the review? Please note that the frequency of reviews should be commensurate with the risk of the study. At a minimum, a review of the data should be conducted annually at time of continuing review. **Forward copies of the data and safety monitoring reports to the 1) IRB, 2) CRC (if applicable), and/or 3) UVMCC (if applicable).**

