Under routine care, patients with dens fractures are monitored for any fracture displacement using x-rays or neurologic changes that require a change in treatment plan. Study participants will be monitored in the same way. For treatment subjects: if the fracture clinic physician [name] has any concerns for abnormal fracture displacement or new neurologic deficit, the PI (or another fellowship-trained orthopaedic or neurologic spine surgeon on the study team as delegated by the PI) will review all radiographic evidence of fracture displacement or neurologic deficit. Based on fracture displacement and neurologic changes, the patient may require a change in their treatment plan. Study patients are treated no differently from non-study patients in this regard. If there is a significant change in their treatment plan (e.g. surgery), these patients will be withdrawn from the study at the discretion of the PI.

All study participants may voluntarily withdraw themselves from the study at any time. If a participant decides to withdraw, the study will continue to use the information already collected for the study before withdrawal. This is noted in the informed consent forms for both control and treatment subjects.

If a patient were withdrawn from the study for any reason, the standard of care treatment for their fracture would resume.

Sources of Materials: Identify sources of research material obtained from individually identifiable human subjects in the form of specimens, records or data. Indicate whether the material or data will be obtained specifically for research purposes or whether use will be made of existing specimens, records or data.

Sources of research information will be provided in the electronic health records (including imaging) and study questionnaires. This information will be used for eligibility screening, safety monitoring, primary outcome (CT scans) and secondary outcome (radiographs, VAS and NDI) measures. Material will be derived from both existing sources in the electronic health record and research-driven procedures. Together these materials include:

For treatment subjects

- Lab results and office notes
- Office notes from clinical exams and consultations, including VAS Neck and NDI measures
- Radiographs and CT scans
- Drug diary

For historical comparison subjects (Control cohort A: active control participants)

- Lab results and office notes
- Study questionnaires (VAS Neck and NDI)
- Radiographs and CT scans

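### The as-treated comparison removes treated patients with an undefined partial course and admits only collar completers as controls, with no analysis rule for conversions to surgery

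*Combined protocol and SAP*

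**What the plan says.** **Treated group.** Statistical Considerations specifies an as-treated analysis of % bridging bone on the 12-week CT, tested at p<0.05. It then says that "if there are patients who receive only partial course of study drug for any reason, they will be evaluated descriptively as a separate group". The course is given in Table 1 as "daily for 8 weeks after drug teaching". Sources of Materials lists a drug diary, but no section links it to a definition of partial.

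**Surgery.** Withdrawal Procedures says that after a "significant change in their treatment plan (e.g. surgery), these patients will be withdrawn from the study at the discretion of the PI". It adds: "If a patient were withdrawn from the study for any reason, the standard of care treatment for their fracture would resume". Neither sentence says how the patient enters the primary analysis.

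**Controls.** Study Design (Control subjects) and the inclusion criteria for Historical Comparison Subjects both require completion of 12 (+/-1) weeks of hard collar. Treated patients are planned for the same collar time, but completing it is not a condition for being analysed.

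**Timing.** The drug starts "at the latest 4 weeks from injury which will allow for completion of 8 weeks of drug administration", and the research CT is taken "at the 12 (+/-1) week time point".

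**The concern.** The hypothesis under Purpose concerns adding the drug to a collar. The planned comparison is between treated patients who finished the drug and controls who finished the collar. Both conditions are met or failed after treatment begins, and they are different conditions.

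If the patients lost differ in healing from those kept, and the losses differ between the groups, the estimated difference mixes drug effect with selection. Surgery for displacement or neurologic deficit is a plausible healing-related loss. A patient withdrawn for it may have no 12-week CT, because that scan is done only for research. With partial undefined, one or two patients could also be classified after their CTs are known. The pilot is meant to suggest efficacy and inform a randomised trial, so a selection effect would carry into that trial's assumptions, and the pilot's confidence interval would not show it.

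**Working it through.** **1. The plan's own figure.** Inputs from Statistical Considerations: 60% vs 20% non-union, alpha 0.05 (two-sided assumed), 80% power. Arcsine formula: h = 2·asin(√0.6) − 2·asin(√0.2) = 0.845; n = 2(1.960 + 0.842)²/h² = 21.99, so 22 per group and 44 in all. The stated 44 reproduces and is not in dispute. The pilot itself has 10 treated and 12 controls.

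**2. Moving one or two treated patients.** The documents give no rate of partial courses or conversions, so these are illustrations. Start from 6/10 non-unions, which is no drug effect at the plan's control rate.

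| Removed from comparison | If non-unions | If united |
|---|---|---|
| none | 6/10 = 60.0% | 6/10 = 60.0% |
| 1 | 5/9 = 55.6% (−4.4) | 6/9 = 66.7% (+6.7) |
| 2 | 4/8 = 50.0% (−10.0) | 6/8 = 75.0% (+15.0) |

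At the plan's target of 2/10, removing one non-union gives 1/9 = 11.1% (−8.9).

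**3. Losses on the control side.** One control non-union kept out beside 12 qualifying controls, 7 of them non-unions: 8/13 = 61.5% becomes 7/12 = 58.3% (−3.2). One such loss in each group nets 4.4 − 3.2 = 1.2 points.

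**4. Losses as rates.** If a share q of non-unions is lost, a true rate p appears as p(1−q)/(1−pq). Take q = 0.3 as an assumption.
- Both groups truly 60%, both losing 30% of non-unions: 0.42/0.82 = 51.2% in each, so no shift.
- True 60% vs 20%, both losing 30%: 51.2% vs 0.14/0.94 = 14.9%. The difference falls from 40 to 36.3 points, slightly against the drug.
- Worst case, both truly 60% with loss in the treated group only: 60 − 51.2 = 8.8 points in the drug's favour. Loss in controls only gives the same shift the other way.

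**5. Against the pilot's noise.** SE at 60% in both groups = √(0.24/10 + 0.24/12) = 21.0 points. Even the one-sided worst case is 8.8/21.0 = 0.42 SE.

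**6. Is the dose count ambiguous?** Daily for 8 weeks is 56 doses. A start at week 4 with a CT at week 11, both within plan, gives 7 × 7 = 49 doses by the CT. The plan does not say whether doses are counted to the CT or to the end of the course.

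**The case against.** The strongest reply is that the one healing-related mechanism works on both sides. Treated conversions may be withdrawn, and controls operated on before completing the collar never enter. Withdrawal Procedures adds that study patients are managed no differently from others in this respect. Steps 3 and 4 bear this out: similar losses largely cancel, or are slightly conservative if the drug works. No section links stopping the drug without surgery to healing, and stops unrelated to healing cost only precision. A prespecified as-treated analysis is also defensible in a 10-patient pilot, particularly as the partial-course patients are still reported. All of this stands. It limits the size of the concern, but it does not define partial or say how conversions count.

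Four stronger readings are tempting, and the documents do not support them:
- *That surgical conversions have no rule and partial-course patients are discarded.* There is a discretionary withdrawal rule; what is missing is an analysis rule. Partial-course patients leave the comparison but are described.
- *That the design favours the drug.* The direction depends on who is lost.
- *That a week-4 starter scanned at week 11 has a partial course.* No section stops the drug at the CT, so that patient can still complete 56 doses. The case shows only an ambiguity. Similarly, that withdrawal ends the drug is an inference from standard care resuming; no section states it.
- *That a later trial of 22 per group would have 62% power instead of 79% and need 33 per group.* This is a worst case. It assumes 30% of treated non-unions are lost and no controls are lost, so that a true 26.3% (0.2/0.76) appears as 20%. The documents give no source for that loss rate, and the control entry rule makes zero control loss hard to assume.

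**Conclusion.** The concern holds in a limited form. Treated patients are selected on an undefined drug-completion rule, controls are selected on collar completion, and treated conversions to surgery have no stated place in the analysis. One or two treated patients can move the apparent non-union rate by about 4 to 15 points in the illustration from 6/10, in either direction. This is well inside the pilot's own uncertainty, and similar losses in both groups would largely cancel.

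The figures rest on assumed loss counts and on the plan's 60% and 20%. They concern union as yes/no, whereas the primary outcome is continuous % bridging. The point is worth fixing because the rule is already written into the plan, the ambiguity can be removed before any CT is read, and the estimate is meant to inform a randomised trial.

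**What to change.** 1. Analyse % bridging in all treated patients who took at least one dose and have a 12-week CT, and report it beside the full-course as-treated analysis. Keep the already scheduled 12-week CT for patients who stop the drug early but remain in the study.
2. Define full course numerically from the drug diary, for analysis purposes, before any CT is read. State the date to which doses are counted.
3. State in advance how patients converted to surgery count, for example as not healed in a sensitivity analysis. This needs a union cut-off on % bridging, which the documents do not give and which should be fixed beforehand. Controls operated on before completing the collar are not in the study, so counting only treated conversions as failures leans against the drug; label the result accordingly.
4. Tabulate by group the numbers started, completed, operated, died and with a CT, and state that the control group is limited to collar completers.

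**Cost.** Mostly protocol wording, plus one follow-up instruction in item 1. The control counts can use the database query and chart review already planned, but only as far as consent allows: living review-only controls need verbal consent, and some may have no CT. The all-dosed analysis will be somewhat diluted if several patients stop early, and it still misses patients with no 12-week CT, which is why items 3 and 4 are needed. No clinical decision on surgery or on stopping the drug changes.
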